#### Transient elastography (Fibroscan®)

Transient elastography examinations will be carried out by a single gastroenterologist (PA) with Fibroscan® (Echosens, France). The examinations will be performed through one intercostal space that provides an optimal unobstructed view to the right lobe of the liver. The results will be based on a median of ten validated measurements. Transient elastography results with an interquartile range (IQR) below 30% of the median value and a success rate of at least 60% will be accepted, according to manufacturer's recommendations.

#### Indirect calorimetry

Indirect calorimetry (Datex Metabolic Monitor, Datex, Helsinki, Finland) will be used to estimate basal metabolic rate from measurements of oxygen (O2) consumption and carbon dioxide (CO2) production. Patient is lying supine in bed, breathing calmly and regularly in the canopy with a constant air flow (to be adjusted to give O2 and CO2 concentrations within workable range). O2 (VO2) consumption, CO2 (VCO2) production, a urinary nitrogen excretion during the study will be measured and on the assumption that all the oxygen is used to oxidize degradable fuels and all the CO2 thereby evolved is recovered, it is possible to estimate the amounts of glucose and lipids oxidized by the body and calculate the basal energy expenditure.

#### Fat biopsy

A subcutaneous fat biopsy (appr. 2-3 g) will be taken under local anesthesia from abdominal area. Biopsy will be taken using mini-liposuction technique. Part of the sample will be immediately frozen and stored in liquid nitrogen or -80°C until used for transcriptional, protein or other biochemical analyses. Another part will be used for measurement of adipocyte size under a light microscope.

#### Fasting blood samples

Routine laboratory tests, including HbA1c, total, LDL and HDL cholesterol, and triglycerides, thyroid function (TSH, T4v) and liver enzymes (AST, ALT, GGT, AFOS) will be collected and analyzed in HUSLAB. B-PNPLA3 sample will be collected and send to Yhtyneet Medix laboratory where the sample will be analyzed for the fatty liver adipose allele. In addition, extra samples of plasma and serum will be stored for further analysis, e.g. for metabolomics, lipidomics, proteomics, hormones, adipokines.

#### Oral Glucose Tolerance Test (OGTT)

OGTT (oral glucose tolerance test) will be performed for all patients after an overnight (10-12 h) fast. A fasting blood sample will be collected after which patients will take a 75 g oral glucose dose in about 5 minutes. Zero time is the beginning of the drink and blood samples are collected at time points 0, 30, 60 and 120 minutes for measurement of plasma glucose, insulin and c-peptide. Extra samples will be collected at each time point for the above mentioned purposes.

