## 2. List of study objectives

Primary objective is:

1. Baseline to 24-week Change in Liver Fat (measured by proton magnetic resonance spectroscopy,  $\Delta \%$ )

Secondary objectives are:

1. Baseline to 24-week Change in Body Composition including subcutaneous and visceral adipose tissue volume (measured by magnetic resonance imaging), total body fat and lean tissue mass (measured by Bioelectrical Impedance Analysis)
2. Baseline to 24-week Change in Liver Stiffness measured by transient elastography (Fibroscan ®)
3. Baseline to 24-week Change in Glucose Metabolism including fasting glucose, insulin, 2-h oral glucose tolerance test
4. Baseline to 24-week Change in Lipid Profile (LDL and HDL cholesterol, Triglyceride)
5. Baseline to 24-week Change in Metabolic and Inflammatory Biomarkers (e.g. high-sensitivity C-reactive protein (hsCRP), adiponectin, etc)
6. To collect subcutaneous adipose tissue samples at baseline and 24 weeks for future gene expression studies
7. To collect stool and saliva samples at baseline and 24 weeks for future microbiome studies
8. To collect safety and tolerability data related to the switch to raltegravir
9. Determination of the fatty liver adipose allele (B-PNPLA3)
10. Determination of basal metabolic rate by indirect calorimetry at screening and at the end of study

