## 3. Study subjects

Actual subject recruitment will start after ethics committee (EC), competent authority (CA) and clinic approvals have been granted. The study subjects will be recruited and screened in a single center (Aurora hospital, Infectious diseases clinic, HUH, Helsinki). All the eligible study subject candidates will be contacted during regular visits and informed of the study by study investigators verbally and with a written information hand out. After adequate time and opportunity to inquire about details of the study and to decide whether or not to participate in the study, the candidates will sign and personally date an informed consent. After the study has finished, all the study subjects will continue their regular follow up with a chance to continue their current ART or to switch to another regimen.

The total number of study subjects included in the study is 45. Study subjects will be randomized 1:1 to continue current ART regimens or to switch their PI or efavirenz to once daily raltegravir

plus continue current NRTIs. The randomization will be stratified by age, sex and antiretroviral regimens (PI or efavirenz).

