## 4. Study procedures and assessments

This study is an investigator initiated, single-center, prospective, randomized, open-label, parallel design study.

Study flow chart consists of

1. Screening visit, signing of the informed consent and randomization
2. Baseline study visit in the Obesity Research Unit with study measurements detailed below in section "Study procedures in Obesity Research Unit".
3. Baseline visit in Meilahti hospital, where MR imaging and spectroscopy, and transient elastography will be done.
4. Visit at the Infectious Diseases Clinic, where the current ART will be continued or modified according to the randomization. Patient follow up will take place according to the standard of care with two safety laboratory tests at weeks 2 and 8.
5. 24 week study visit in the Obesity Research Unit with the same study measurements as detailed at the baseline (see section below).
6. 24 week study visit in Meilahti hospital, where MR imaging and spectroscopy, and transient elastography will be repeated.
7. End of study visit (24 weeks after study start) at the Infectious Diseases Clinic, where current ART can be continued or modified according to the standard of care.

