## 6. Data analysis

The data will be analyzed by the investigators and the study group.

All variables of the data will be analyzed after the last subject's last visit, when the data have been declared complete.

The data will be analyzed using IBM SPSS Statistics v. 22. The differences between the groups will be analyzed by using chi-square, Fisher's exact, Mann-Whitney U test and others, as appropriate.

As there are no earlier ART-switch studies using H-Magnetic resonance spectroscopy for the quantification of liver fat, the calculation of the study power is an estimate. In the STERAL study evaluating the effect of switching from efavirenz (EFV) to RAL vs. continuing Efv-based ART, a statistically significant difference in the liver fat content using CAP (controlled attenuated parameter) was shown with a study sample of 19 +18 subjects after 48 weeks (7,3% decrease in the RAL vs. 11,0% increase in the Efv arm, p = 0,019) (11).

The power of this study is calculated with the assumption of liver fat being 4.4-5.0% in this study group at baseline. This estimation is based on our previous results published in 2002, when the median liver fat was 8% with lipodystrophic patients and 3% with non-lipodystrophic patients (17). Hadigan et al reported liver fat content being >5% in 42% of HIV positive subjects (18). As the liver fat content correlates with visceral fat mass, studying overweight or obese patients with at least one metabolic syndrome component includes patients at high risk for elevated liver fat content.

In the power calculation, we have used a coefficient of variation (CV) of H-Magnetic resonance spectroscopy being 11% (17). To detect a 9% difference between study arms with 80% power, a minimum sample size of 25 + 25 subjects with a 10% drop-out rate is needed.

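### Secondary objective 3 does not say which OGTT values are compared between arms, so the choice among up to twelve correlated changes, or any summary of them, stays open until the data are complete

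*Combined protocol and SAP*

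**What the plan says.** All references are to the combined protocol and SAP.

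- **Section 4.3, Oral Glucose Tolerance Test:** "blood samples are collected at time points 0, 30, 60 and 120 minutes for measurement of plasma glucose, insulin and c-peptide".
- **Section 4, study flow chart:** the test is repeated, since the plan has a "24 week study visit in the Obesity Research Unit with the same study measurements as detailed at the baseline".
- **Section 2, secondary objective 3:** "Baseline to 24-week Change in Glucose Metabolism including fasting glucose, insulin, 2-h oral glucose tolerance test". The wording leaves the list open. It gives no time point for insulin and no analyte for the 2-h test. It does not mention C-peptide or the 30- and 60-minute samples.
- **Section 6, Data analysis:** "The differences between the groups will be analyzed by using chi-square, Fisher's exact, Mann-Whitney U test and others, as appropriate". On timing: "All variables of the data will be analyzed after the last subject's last visit, when the data have been declared complete".
- **Publication plan:** secondary objectives 1 to 3 go into the main manuscript with the primary result.

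No section defines an area under the curve, an insulin-sensitivity or secretion index, a repeated-measures model, a baseline-adjusted model or a multiplicity rule.

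**The concern.** A sampling scheme this rich can be turned into many different results. Two of the three items in objective 3 can be read in more than one way. Insulin could be fasting, 120-minute or the whole series. The 2-h test could mean the 120-minute glucose value or everything collected over two hours. The trial is open-label and the investigators analyse it themselves once all data are in, so nothing written in advance limits which reading is reported.

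Interpretation is also at stake. A fall in insulin on its own may reflect better sensitivity or weaker secretion. The glucose drawn at the same moment helps to separate the two, but the plan does not say that the pairs will be used together. Because objective 3 is meant for the main paper, an unplanned choice here could appear beside the primary result as a metabolic benefit.

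**Working it through.** **Plan's own figure.** The plan gives no calculation for the OGTT. Its only sample-size figure concerns liver fat, where the target is a 9% difference at 80% power and the conclusion is that "a minimum sample size of 25 + 25 subjects with a 10% drop-out rate is needed". Taking the stated CV of 11% as the SD and assuming two-sided 5%, the normal formula gives 2 x (1.96 + 0.84)^2 x (11/9)^2 = 23.4, so 24 per arm. The exact t-test gives 24.4, so 25 per arm. The figure of 25 is thus reproduced as evaluable subjects. Nothing below depends on it.

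**Step 1: the count.** Four times x three analytes = 12 values per test. Two tests per subject give up to 12 baseline-to-week-24 changes.

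**Step 2: chance of at least one false positive.** The documents state neither the significance level nor the correlations, so both are assumptions: two-sided 5% and equal pairwise correlation. For k independent tests the chance is 1 - 0.95^k. For correlated tests it was simulated with 200,000 sets of equally correlated z-statistics.

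| Correlation | 3 tests | 12 tests |
|---|---|---|
| 0 (formula) | 14.3% | 46.0% |
| 0.3 | 13.7% | 39.9% |
| 0.5 | 12.5% | 31.9% |
| 0.7 | 11.0% | 23.1% |
| 0.9 | 8.4% | 13.5% |

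A separate simulation of twelve t-tests with 22 subjects per arm gave 40%, 33% and 24% at correlations 0.3, 0.5 and 0.7, which agrees. A single prespecified measure gives 5%. Bonferroni over twelve would need 0.05/12 = 0.0042 per test.

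**Step 3: what a glucose AUC could add.** The trapezoid rule over 0, 30, 60 and 120 minutes gives weights (15, 30, 45, 30)/120.

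- Sum of squared weights: (225 + 900 + 2025 + 900)/14400 = 0.281.
- Assume equal SDs of change and common correlation rho. The variance of the AUC mean relative to one time point is 0.281 + 0.719 x rho.
- At rho = 0.5 this is 0.64, an SD ratio of 0.80. At rho = 0.3 the SD ratio is 0.70, and at rho = 0.8 it is 0.93.
- The comparison also depends on the size of the shift. At rho = 0.5 the 120-minute value does as well as the AUC when its shift is 1/0.80 = 1.25 times the weighted mean shift. Beyond that the AUC loses power.

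**The case against.** The best defence is that the plan never commits to a bad analysis. Several stronger readings are tempting, and the documents do not support them.

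- **Twelve separate tests, or the 2-h value alone with the rest discarded.** Objective 3 also names fasting glucose and insulin, so more than the 2-h value is used on any reading. No section says that twelve changes will be tested. The open wording in objective 3 and section 6 allows an AUC, an index or a model.
- **A 46% false-positive rate.** This needs twelve independent tests. Serial samples from one test in one person are correlated, so 46% is an upper bound. For the three named items the figure is 14.3% at most.
- **A loss of precision equal to 56% more subjects.** That is 1/0.64 = 1.56. It needs correlation 0.5, equal SDs and the same shift at every time point, including fasting. The documents support none of these.
- **Insulin cannot be interpreted.** Both analytes are drawn together, and nothing rules out joint use. The gap is only that no such use is stated.

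It is also fair to say that this is one of ten secondary objectives, and one instance of a generic analysis sentence.

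All of this limits the size of the point but does not remove it. The same open wording that permits a good summary also permits choosing one after the results are known. The plan collects what it needs for a clear answer and does not say how it will be used.

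**Conclusion.** The point holds as a gap in specification. Objective 3 leaves the time point for insulin and the analyte for the 2-h test unstated. It gives no role to C-peptide or the intermediate samples, and no rule for choosing among up to twelve correlated changes. The named tests make no use of the baseline value as a covariate.

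Testing all twelve would carry a false-positive chance of about 14% to 40% at correlations of 0.9 to 0.3. The three named items carry about 12% to 14% at correlations up to 0.5, and less above that. These figures rest on an assumed two-sided 5% level and assumed equal correlations. Any precision gain from an AUC is conditional on equal SDs and similar shifts across time points.

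The plan should be changed because the remedy is nearly free and the result is intended for the main paper. The primary liver-fat analysis is unaffected.

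**What to change.** Amend objective 3 and section 6 before the data are analysed.

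1. Keep the named measures and state them exactly: fasting glucose, fasting insulin and 120-minute glucose. If another time point or analyte was intended, name it.
2. Add two prespecified summaries from samples already taken: glucose AUC from 0 to 120 minutes by the trapezoid rule, and one insulin-sensitivity index from paired glucose and insulin (for example the Matsuda index). The inclusion criteria admit subjects on diabetes medication, so state how any insulin-treated subjects are handled in the index.
3. Compare each of the five measures once between arms, in a model adjusted for its own baseline value, on a log or rank scale if skewed.
4. Label C-peptide and all other time points exploratory.

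The cost is a few sentences and a little more analysis, with no new samples or visits. The drawback is two more secondary measures. Five unadjusted comparisons would give 1 - 0.95^5 = 22.6% if independent, and less if correlated. They should therefore be reported as secondary estimates with confidence intervals, and a single significant result among them should not be presented as proof of benefit.

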### Saliva

Saliva will be collected after stimulation by chewing parafilm. Saliva samples will be stored for later purposes and can be used e.g. for microbiota, cortisol, and metabolomics analyses.

### Feces

Feces will be collected either at home or at the research center. Collection specimen and instructions will be given during the first visit. Feces samples can be used later to analyze the fecal metabolites, including fatty acid composition and the microbiota.

### Urine

Urine samples will be collected on a study morning to perform a pregnancy test for females at childbearing age. Additionally urine samples can be stored for later analyzes, e.g. metabolomics.

## 5. Safety assessments and ethical considerations

### **5.1. Study sites and study procedures**

The investigator is responsible for ensuring adequate medical expertise and facilities to conduct the study and to handle possible emergency situations during the study. All procedures and possible hazards, risks and discomforts are explained to the subjects both verbally and in writing (see informed consent).

For the blood sampling, a forearm vein will be cannulated. In this study, the maximum volume of blood drawn per subject during the visits in Obesity Research Unit will be approximately 300 ml.

There is no ionizing radiation in MRI/MRS/ transient elastography studies.

The subcutaneous abdominal fat biopsies will be taken under local anesthesia with sterile conditions. The needle used for local anesthesia can cause slight discomfort but the biopsies themselves are painless. A fat biopsy will be taken using a mini-liposuction technique. The incision is closed with skin tape and covered by pressure bandages. The subjects will be advised to avoid strenuous exercise for two days after the procedure. The biopsy site might have a dull ache for 24-48 h for which the subjects are provided pain-killers. However, medications such as aspirin, or ibuprofen are not recommended since they may contribute to bleeding and/or bruising during the post-biopsy period.

Study subjects may experience moderate discomfort from the blood samples and biopsies.

The subjects will have to reserve two days for the study visits in Obesity Research Unit besides the normal follow up in Aurora hospital. Travel costs incurred as a result of a study visit will be reimbursed on the basis of supporting documents according to actual costs.

Study personnel will conduct all procedures according to GCP (good clinical practice) guidelines. In the case of a needle stick injury, personnel is advised to contact immediately the study investigator or the infectious diseases specialist on duty in the Infectious Diseases Clinic for the evaluation of the need for HIV post exposure prophylaxis.

## 5.2 Raltegravir

Raltegravir (trade name Isentress®) is an HIV medicine that is used in combination with other HIV medicines to treat adults and children who are infected with human immunodeficiency virus (HIV-1). It is developed and manufactured by Merck Sharp & Dohme Corp (MSD). The European Commission granted a conditional marketing authorisation valid throughout the European Union for Isentress on 20th December 2007. This was switched to a full marketing authorisation on 14th July 2009. A new formulation of Isentress 600mg coated tablets was granted a marketing authorisation by European Comission on 18th July 2017. The recommended daily dose for the new formulation is 1200 mg (two 600 mg tablets) once daily. In this study, we plan to use the once daily formulation of raltegravir. This study drug is provided by Merck Sharp & Dohme Corp.

Raltegravir is one of the best tolerated HIV-medicines. The most common reported adverse effects with Isentress (seen in between 1 and 10 patients in 100) are abnormal dreams, nightmares, insomnia, depression, abnormal behavior, dizziness, headache, psychomotor hyperactivity, vertigo, decreased appetite, abdominal distension, abdominal pain, diarrhea, flatulence, nausea, vomiting, dyspepsia, rash, asthenia, fatigue, pyrexia, atypical lymphocytes, and increased blood levels of some enzymes (alanine aminotransferase, aspartate aminotransferase, lipase and pancreatic amylase) and triglycerides. For more details of the study drug, see SmPC of Isentress attached.

## 5.3. Adverse events assessment

**An AE** is any untoward medical occurrence in a study subject administered a pharmaceutical product and which does not necessarily have a causal relationship with this treatment. An AE can therefore be any unfavourable and unintended sign (including an abnormal laboratory finding), symptom, or disease temporally associated with the use of an investigational medicinal product (IMP), whether or not related to the IMP. The definition also covers medication errors and uses outside what is foreseen in the protocol, including misuse and abuse of the product.

Thus, an AE may be an appearance or worsening of any undesirable sign or symptom, any worsening of the current medical conditions or onset of a new disease, compared with the previous observations or a clinically significant adverse change in a laboratory variable or other diagnostic finding.

**A serious adverse event (SAE)** is any untoward medical occurrence that

- results in death
- is life-threatening
- requires inpatient hospitalization or prolongation of existing hospitalization
- results in persistent or significant disability/incapacity
- is a congenital anomaly/ birth defect, or
- is an important medical event jeopardizing the patient or requiring intervention to prevent serious outcome (examples of such are intensive treatment in an emergency room, convulsions that do not result in hospitalization, etc.)

Any case of pregnancy during a clinical study will be reported by the investigator in the same way as an SAE.

**Other significant AEs** are AEs (other than those meeting the definition of serious) that are of clinical importance and lead to:

- a diagnostic or therapeutic intervention
- discontinuation of the IMP

- significant additional concomitant treatment, or
- marked hematological and other laboratory abnormalities

**Suspected Unexpected Serious Adverse Reaction** or “**SUSAR**” shall mean any Serious Adverse Event, the nature, severity or frequency of which is not consistent with information in the most current Summary of Product Characteristics (SmPC) or Package Insert.

All AEs must be elicited, documented and reported by the investigator. The investigator will assess and record the causality and severity of the AEs due to IMP (see criteria for causality and severity below). SAEs and other significant AEs should be followed up until resolved or until the event is considered a chronic or stable outcome, or both.

The investigator is responsible for expediting all suspected unexpected serious adverse reactions (SUSARS) as well as other safety issues requiring expedited reporting to the relevant authorities within applicable timelines.

Principal Investigator shall forward to MSD’s Global Safety (“MSD GS”) group, any SAE and SUSAR or Incident information, including, but not limited to, all initial and follow-up information involving any study subject in the study. Notification shall be in the form of a completed CIOMS I/MedWatch (or other mutually agreed upon format) within two (2) business days of learning of the information.

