**Causality criteria:**

*Related to the IMP:* The temporal relationship of the AE/SAE onset to the administration of the IMP makes a causal relationship possible, and other drugs, therapeutic intervention or underlying conditions do not provide a sufficient explanation for the AE/SAE.

*Not related to the IMP:* The temporal relationship of the AE/SAE onset to the administration of the IMP makes a causal relationship unlikely, or other drugs, therapeutic interventions or underlying conditions provide a sufficient explanation for the AE/SAE.

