### Publication plan

We anticipate to submit one main manuscript with the results of the primary objective (liver fat change) and secondary objectives (1-3: body composition change as well as metabolic markers). Additional manuscripts will be submitted after further analysis of subcutaneous fat samples (for transcriptional, protein and other biochemical analyses), fecal samples (microbiota) and blood samples (inflammatory markers and metabolomics studies).

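### Section 5.3 ties severity and causality recording to AEs due to the IMP, leaving it unclear whether control-arm, procedural and unrelated events get a severity grade

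*Combined protocol and SAP*

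**What the plan says.** Collection is broad. Section 5.3 of the combined protocol and SAP states "All AEs must be elicited, documented and reported by the investigator". It defines an AE as "any untoward medical occurrence in a study subject administered a pharmaceutical product" and counts events "whether or not related to the IMP".

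The instruction on grading is narrower: "The investigator will assess and record the causality and severity of the AEs due to IMP". The same sentence points to the criteria that follow. The causality criteria have two categories, related and not related to the IMP. The severity criteria have three levels, defined by how far the event affects normal activity.

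Section 5.3 spells out the abbreviation IMP but ties it to no named product. Section 5.2 calls raltegravir the study drug, and no other product is called that. Under section 3 the control arm continues its current regimen. The safety objective, number 8 in section 2, reads "To collect safety and tolerability data related to the switch to raltegravir".

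**The concern.** Two adjacent sentences have different scopes: the first covers all AEs, the second AEs due to the IMP. The second is the only instruction in the document to record severity. If site staff or the designers of the AE form follow it as worded, the control arm has no severity data. In the raltegravir arm, severity data would then depend on a relatedness judgement by an investigator who knows the allocation, since section 4 describes the study as open-label.

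A tabulation of mild, moderate and severe events by arm would then be unavailable, or would compare sets of events selected differently in the two arms. Severity that was not recorded at the time is hard to reconstruct reliably afterwards.

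**Working it through.** The plan gives no figure on this point and no arithmetic applies. The check sets the passages side by side.

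1. **Which events are documented?** All of them (section 5.3). Recording starts at consent for every subject (section 4.1). AEs are asked about at weeks 2, 8 and 24 on one schedule for both arms (section 4.2, Table 1). Serious AE information is forwarded for any study subject (section 5.3). None of this depends on arm or relatedness.

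2. **Which events are graded, read literally?** Those due to the IMP. Taking the IMP to be raltegravir, three groups fall outside:
   - Every event in a control subject. Allocation is 1:1, so this arm is about half of those randomised.
   - Every event from a baseline procedure, in either arm. Section 4.3 places the first Obesity Research Unit visit, which includes the fat biopsy, before the change of treatment. Section 5.1 expects some discomfort from blood sampling and biopsies. Such events are recorded, because recording starts at consent, but they cannot be due to a drug not yet taken.
   - Every raltegravir-arm event judged unrelated.

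3. **Does the literal reading hold together?** No. An event is due to the IMP only once causality has been judged, so the sentence makes the result of the assessment a condition for doing it. The criteria it points to include a not-related category, which begins "The temporal relationship of the AE/SAE onset to the administration of the IMP makes a causal relationship unlikely". That category would never be used if causality were recorded only for events already attributed to the IMP. Causality must therefore be judged for events that turn out to be unrelated.

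4. **Does the not-related category also settle severity?** No. It shows that causality is judged more widely than the sentence says, but not that severity is graded for the events placed in it. The severity criteria define the levels without saying which events receive one.

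5. **Does the causality scale work in the control arm?** Not as it stands. Both categories start from the timing of onset relative to administration of the IMP. If the IMP is raltegravir, a control subject has no such administration. The related category also requires that "other drugs, therapeutic intervention or underlying conditions do not provide a sufficient explanation for the AE/SAE", which does not help with a subject who never took the drug.

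6. **Does the analysis section resolve it?** No. Section 6 names general tests for group differences but sets out no summary of AEs by arm or severity.

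No sentence says that control-arm or unrelated events are left ungraded, and none says that they are graded. Both readings are open.

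**The case against.** The strongest reply is that the sentence is loosely worded and was meant as: grade severity, and judge causality with respect to the IMP. Much supports this. The not-related category makes little sense otherwise. The severity scale mentions neither drug, arm nor cause. The AE definition includes unrelated events. The definition of a suspected unexpected serious adverse reaction compares the severity of any serious AE with the product information, without first requiring attribution to the drug. This reply largely stands as evidence of intent, and it disposes of any claim that causality is recorded only for related events. It does not supply the missing instruction on severity, and a form designer could reasonably follow either reading.

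A second reply is that objective 8 is to collect data on the switch and states no comparison of graded events between arms. That is correct, and it limits the consequence. It does not remove the need for a clear recording rule in a randomised trial whose control arm is followed on the same AE schedule.

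**Conclusion.** The point holds as a wording defect that must be reconciled, and it is minor. At risk is the severity breakdown for control-arm events, procedural events and events judged unrelated. This rests on taking raltegravir as the IMP, which section 5.2 supports but section 5.3 does not state.

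A reader might infer two stronger things that the documents do not support:

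- **That graded safety data will exist in one arm only, so that the randomised safety comparison is lost.** The text contains no word such as only or never. Counts of any AE and of serious AEs are collected in both arms whatever the cause, and most criteria for other significant AEs do not depend on the IMP. Those comparisons remain available.
- **That the rule would produce a false harm signal, because control events would count as zero.** A documented but ungraded event has a missing grade; it is not a non-event. The plan also specifies no test of graded events. No numerical size can be attached to the defect from the documents.

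**What to change.** In section 5.3, replace the sentence on causality and severity with: *Severity is recorded for every AE in both arms whatever its cause; causality is assessed separately for every AE.*

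Define IMP by product name in the same section, and say how the causality field is completed for a subject who does not take that product.

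In section 6, add that AEs, including by severity, are summarised by randomised arm irrespective of causality.

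The cost is a few sentences and, if the AE form does not already have it, a severity field completed for all events. No visit, test or extra contact is needed, because the events themselves are already collected. The change should be made before data collection, since missing grades are hard to recover later.
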